7.2. Scientific background

VTE is a condition of forming a blood clot in the deep veins of the arm, groin, leg, jugular, caval, renal, and portal veins (known as deep vein thrombosis [DVT]). It may travel through the circulation and occlude the pulmonary vasculature (known as pulmonary embolism [PE]).

In the paediatric population, VTE is a rare condition, with an incidence of about 100 times lower than in adults. The annual incidence of VTE has been reported between 0.14 and 0.49 per 10,000 children in the community overall, and between 5.3 and 5.7 per 10,000 among hospitalized children (2). The distribution of events is bimodal with the majority occurring in neonates/infants and in adolescents. Paediatric VTE is rarely idiopathic; more than 80% of children who experience a VTE have one or more risk factors. The most important risk factor is the presence of a central venous catheter. Other factors include infection, immobility, trauma, malignancy, congenital heart disease, chronic inflammatory conditions, and thrombophilia (3). Risk factors for recurrent VTE include age at onset, absence of anticoagulant treatment, persistent venous occlusion, or presence of the prothrombin gene mutation (4). The risk of recurrence for paediatric VTE ranges from 7% to 20%, however, recurrence is uncommon if the underlying cause is removed or resolved.

The aim of VTE therapy is generally to prevent disease progression, prevent VTE recurrence and the development of sequelae such as post thrombotic syndrome. The type of anticoagulation and optimal duration of therapy in the paediatric population is not clearly defined. Due to a moderate level of evidence, treatment guidelines for paediatric VTE are mainly extrapolated from adult studies. The

current SOC includes parenteral treatment with unfractionated heparin (UFH) or low molecular weight heparin (LMWH) and oral anticoagulation with vitamin K antagonists (VKA). For children with idiopathic VTE, the suggested treatment duration has a minimum of 3 months and a maximum of 6 to 12 months. Children with recurrent unprovoked VTE are usually treated indefinitely(5).

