9.2.3. Selection criteria

9.2.3.1. Inclusion criteria

Participants are eligible to be included in the study only if all of the following criteria apply:

- Evidence of initiation of an anticoagulant therapy (index drug), either rivaroxaban oral suspension or other anticoagulation therapies (heparins, VKAs, other DOACs). Initiation will be defined as a first record of any anticoagulation therapy (rivaroxaban or SOC) without any anticoagulation therapy in the previous 6 months, or since date of birth for children less than 6 months (see codes for anticoagulant drugs in [Annex 3](#)).
- Evidence of a prior VTE diagnosis (index VTE), defined as the presence of at least one primary/main or secondary diagnosis code for VTE recorded in inpatient setting in the previous 30 days (see preliminary list for VTE codes in [Annex 3](#)).
- Age less than two years on index date.
- Baseline period for availability of patient data history in the data source. A minimal baseline period of six months before index date for children aged between six months and two years, and a baseline period since birth for children less than six months of age will be required.

According to its indication, rivaroxaban oral suspension should be used after at least five days of initial parenteral anticoagulation treatment. In order to describe the actual clinical practice in real world settings, there will no requirement on this initial parenteral anticoagulation treatment to include patients in the study population, so patients will be identified independently of this. In theory, all patients receiving rivaroxaban should be switchers. In practice, they may appear as initiating directly with rivaroxaban: the observed initial anticoagulant therapy might be different from the actually received initial therapy, if patients have switched drug during hospital stay and if inpatient drug data is not captured. Depending on availability of inpatient drug data in each data source, the observed initiation of the anticoagulant therapy will be identified either in outpatient or in inpatient setting, as shown in [Figure 2](#) below (see [Section 9.4](#)).

SOC for treatment of VTE in children usually include UFH, LMWH and VKA and may vary across countries. With other DOACs receiving indication for VTE in paediatrics, SOC may also evolve over time.

Figure 2 Visualization of patient journey

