9.9. Limitations of the research methods

The use of secondary data that has not been primarily collected for research purposes comes with specific limitations.

Selection bias

- All patients fulfilling eligibility criteria will be included in the study. The data sources in the different countries differ in terms of contents and expected coverage. Most have a national coverage, while SIDIAP which only covers ~75% of Catalonia is also considered representative of the Spanish population. Therefore, the selection bias is considered to be low with respect to the target countries.

Information bias

- Exposure data
 - Anticoagulation therapy is expected to be initiated during hospital stay and renewed for outpatient use. According to its indication, rivaroxaban oral suspension should be used after at least five days of initial parenteral anticoagulation treatment. Thus, in theory, all patients receiving rivaroxaban should be switchers from parenteral anticoagulant treatment. In practice, the capacity to observe the actual initial parenteral anticoagulation treatment and its duration will depend on the availability of inpatient drug data in the selected data sources. This will be feasible when

inpatient drug data is captured, e.g., in the Danish SMR (soon available, with data collected since May 2018) and in SIDIAP through linkage with hospital dispensation medication. However, inpatient drug data is not captured in SNDS and in Swedish national registers, which represents a risk of exposure underestimation. In this latter situation, the information on anticoagulation therapy and its duration will be based on outpatient prescriptions only, at a time when patients may have already, or not yet, stopped the initial parenteral anticoagulation treatment, and switched to maintenance therapy like rivaroxaban. Hence, when patients will have switched to rivaroxaban during hospital stay in an unobservable period in the data source, they will appear as initiating anticoagulation therapy with rivaroxaban, and not switchers. To avoid immeasurable time bias, the index date will be the first observed record of anticoagulation therapy in each data source, whether it occurs during inpatient stay or afterwards.

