The register will contain information on drugs administered to patients while admitted to hospital or during outpatient visits: the date and time of administering the drug, the dose administered via number of units and strength per unit, product name, ATC code, and department information. Thus, this register will complement the RMPS. Data has been captured since May 2018.

It is expected that the register will be updated monthly with a lag of approximately 2 months. However, the register is not yet released for research. Current expectations are that it will be released during 2022.

- Danish National Patient Register (DNPR)

The DNPR contains information on the Danish population's encounters at hospitals (secondary care) (26, 27). Data on activities and diagnoses in primary care at general physicians and specialists in private practice is not included. The register contains information on date and type of admissions and outpatient visits, discharge date and diagnoses, treatments, examinations, surgeries and procedures, including Diagnosis Related Group (DRG) costs.

Data is available from 1977 and onwards for inpatient somatic admissions. Since 1995, outpatient visits, emergency room visits, and encounters at psychiatric wards are included, too. DRG costs have been available since 2002. At Danish Health Care Authority, the register is updated once a month, typically with a lag of approximately 2 months. But if the project requires that data are stored at Statistics Denmark because of link to socio-economic registers, the register is updated once a year after end of December with a lag of approximately 10 months.

Since 1994, ICD-10 has been used as classification system. ICD-8 was used between 1977 and 1993.

- Danish Medical Birth Register (MBR)

The Danish MBR is an enrichment of data already recorded in the National Patient Register (NPR) and compiles relevant information of pregnancies that has led to childbirth in Denmark at home or in a hospital. It contains information on characteristics of mother and child, pregnancy, and delivery characteristics including induction procedures and gestational age, outcomes of pregnancy and delivery, and the mother's history of previous abortions and/or deliveries. MBR includes linkage between infant, mother and father.

- Danish Register of Causes of Death

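### Where inpatient drugs are visible, the 6-month washout may exclude or mis-index children given hospital heparin before the VTE code, so eligibility depends partly on the data source

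*Protocol*

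**What the plan says.** Section 9.2.3.1 fixes two conditions that act together. Initiation is a "first record of any anticoagulation therapy (rivaroxaban or SOC) without any anticoagulation therapy in the previous 6 months"; for children under 6 months the look-back runs to birth. The child must also have "at least one primary/main or secondary diagnosis code for VTE recorded in inpatient setting in the previous 30 days", counted back from that initiation.

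Section 9.3.1 identifies study drugs by ATC code. The Annex 3 list includes heparin (B01AB01) and the low molecular weight heparins, with no restriction by dose, route or purpose.

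The setting of initiation differs by source: "the observed initiation of the anticoagulant therapy will be identified either in outpatient or in inpatient setting". Section 9.9 expects hospital drug data "in the Danish SMR (soon available, with data collected since May 2018) and in SIDIAP through linkage with hospital dispensation medication". Annex 3 describes SMR as holding "information on drugs administered to patients while admitted to hospital or during outpatient visits". For the other two sources, section 9.9 says that "inpatient drug data is not captured in SNDS and in Swedish national registers".

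Section 9.9 discusses this gap under exposure data, as a reason why switchers may look like initiators. Under selection bias it rates the risk as low and does not mention the gap. Section 9.7.8 expects that characteristics and drug-use results can be combined across sources.

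**The concern.** The first condition counts every listed anticoagulant record. The second requires the VTE code to come before the index record. A hospital heparin record dated before the VTE code satisfies neither role: it cannot be the index, because no VTE precedes it, and it makes the later start of treatment fail the washout.

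The protocol's own background makes this sequence plausible. Section 7.2 says: "The most important risk factor is the presence of a central venous catheter". Section 9.3.2.2.2 expects VTE to be coded often as a complication of a stay for another reason. Catheter use, major surgery and intensive care are also baseline characteristics to be reported (section 9.3.2.1.1), so the washout may select on the variables that the study sets out to describe.

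The effect can arise only where hospital drugs are seen. A difference between countries in characteristics or initial therapy could then reflect what the source records rather than the children or their care, and the combined description would mix differently filtered cohorts.

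**Working it through.** **Step 1. The rules applied to one child.** The dates are illustrative: admission day 0, heparin not for VTE treatment on day 1, VTE arising and treated from day 15.

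| Source view | VTE code dated | Outpatient fill | Result |
|---|---|---|---|
| Inpatient drugs visible | day 15 | any later day within 6 months of day 1 | Day 1 has no prior VTE code. Day 15 and later fail the washout (15 − 1 = 14 days). **Excluded.** |
| Inpatient drugs visible | day 0 (admission) | any | Day 1 has a code 1 day earlier and a clean washout. **Included, indexed on the day-1 heparin**, which counts as SOC. |
| Outpatient only | day 15 | day 25 | Code 25 − 15 = 10 days earlier. **Included**, index day 25. |
| Outpatient only | day 15 | day 50 | Code 50 − 15 = 35 days earlier, over 30. **Excluded.** |

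The outpatient-only rows assume no earlier outpatient anticoagulant. The protocol does not say whether an inpatient VTE code takes the admission, discharge or event date, so both of the first two rows are possible.

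**Step 2. Reproducing the plan's counts.** Inputs are the average numbers of children with VTE in Table 6 and the six annual market shares in section 9.5.2. Mean share = (10 + 32 + 38 + 42 + 50 + 30)/6 = 202/6 = 33.67%.

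- Denmark: 52 × 0.3367 = 17.5 (stated 18)
- SNDS: 650 × 0.3367 = 218.8 (stated 219)
- SIDIAP: 45 × 0.3367 = 15.2 (stated 15)
- Sweden: 98 × 0.3367 = 33.0 (stated 33)
- Overall: 846 × 0.3367 = 284.8 (stated 285)

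The figures reproduce. They are built from incidence, age share, population, coverage and market share. No step allows for children lost to the washout.

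**Step 3. The most the rule can touch.** Denmark plus SIDIAP: 52 + 45 = 97 of 846 (11.5%); on rivaroxaban 18 + 15 = 33 of 285 (11.6%).

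**Step 4. Range for an unknown loss.** The documents do not give the share with earlier hospital heparin. The loss *f* below is an assumption, taken as equal in both sources and in rivaroxaban users. Remaining = count × (1 − *f*); overall = 846 − 97*f* and 285 − 33*f*.

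| *f* | Denmark VTE / rivaroxaban | SIDIAP VTE / rivaroxaban | Overall VTE (lost) | Overall rivaroxaban |
|---|---|---|---|---|
| 10% | 46.8 / 16.2 | 40.5 / 13.5 | 836 (1.1%) | 282 |
| 25% | 39.0 / 13.5 | 33.8 / 11.3 | 822 (2.9%) | 277 |
| 50% | 26.0 / 9.0 | 22.5 / 7.5 | 798 (5.7%) | 269 |
| 80% | 10.4 / 3.6 | 9.0 / 3.0 | 768 (9.2%) | 259 |

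Section 9.4.1 chose sources with an estimate of at least 15 rivaroxaban-exposed children. SIDIAP's stated estimate is exactly 15, so losing even one child puts it below. Denmark goes below when 18 × (1 − *f*) < 15, that is *f* > 3/18 = 16.7%.

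**The case against.** Several points on the other side are sound.

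- **Not a permanent bar.** A reader might infer that a child with prior hospital heparin can never qualify. The protocol does not support that. The child enters if the heparin was more than 6 months earlier, if the VTE code is dated within 30 days before the first heparin record, or at a later VTE treated after a clean 6 months and before age two (section 9.2.2.1).
- **No automatic entry elsewhere.** A reader might also infer that the identical child always enters in SNDS or Sweden. The last row of the first table shows otherwise.
- **Contingent data.** Annex 3 says SMR was not yet released for research, and Table 3 calls the SIDIAP hospital linkage possible. No section says that line-patency heparin is recorded in either.
- **Limited reach.** Section 9.7.8 expects bleeding and recurrence analyses to be feasible only in SNDS, so those results are little affected.
- **Partly visible already.** Analyses run by source (section 9.7.1), section 9.7.2 plans an attrition display, and the SAP will define exposure variables in detail.
- **The present washout has merit.** It uses the best data each source has. An outpatient-only washout as the main rule would discard observed inpatient data and loosen the new-user and re-entry rules. Indexing on the first record after admission could again select non-treatment heparin.

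These points limit the size of the problem and argue against replacing the main criterion. They do not remove it. The criterion itself is fixed in the protocol, no section exempts any heparin record, and by-source reporting does not make cohorts comparable when they were filtered differently and are then combined.

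**Conclusion.** The point holds in a limited form. As written, eligibility and index date depend partly on whether the source records hospital drugs. In Denmark and SIDIAP, a child with hospital heparin recorded before the VTE code and within 6 months may be excluded, or may be indexed on non-treatment heparin if the code is dated at admission. In SNDS or Sweden a similar child can enter if an outpatient fill falls within 30 days after the code. Section 9.9 should list this as selection bias and does not.

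The reach is at most about 97 of 846 expected children (33 of 285 on rivaroxaban). The share actually affected is unknown. The consequence falls on two primary objectives, patient characteristics and drug use, and on their combined analysis. It rests on SMR being released, SIDIAP being linked, and such heparin being recorded there.

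A reader might go further and conclude that the children who remain are healthier or bleed less. The documents give no data on that.

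**What to change.** 1. Keep the present washout in section 9.2.3.1 as the main rule.
2. For Denmark and SIDIAP, add a harmonised cohort in which both the washout and the index drug use outpatient-dispensed anticoagulants only, as in SNDS and Sweden. SMR records from hospital outpatient visits should not count as dispensing here. Keep the 6-month washout over all records for re-entry, so that a child treated only in hospital is not soon counted again as a new initiator.
3. Use the harmonised cohort for cross-source comparison and for the combined characteristics and drug-use analysis (section 9.7.8).
4. State how an inpatient VTE code is dated in each source.
5. Describe earlier inpatient heparin as a baseline characteristic where it is visible.
6. Report washout exclusions by source in the attrition table (section 9.7.2).
7. Name this selection effect in section 9.9.

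The cost is some added text before data extraction and one extra cohort in two sources. The downside is that members of that cohort are not strictly heparin-naive.

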9.2.3.2. Exclusion criteria

Participants are excluded from the study if any of the following criteria apply:

- None.

9.2.4. Representativeness

The paediatric patients with VTE documented in the country/source databases will be selected only based on eligibility according to inclusion and exclusion criteria. No further selection will be applied.

By abstracting the patient details in routine clinical practice from the population-based data sources of different countries, the study is expected to be representative for different geographical locations and health care systems. Moreover, each planned data source is considered representative of the corresponding country's population.

9.3. Variables

9.3.1. Exposure

- Information on exposure will be ascertained based on recordings of issued prescriptions, prescriptions dispensed at community pharmacies, or insurance claims registrations, according to availability and contents of data in each of the different data sources. For simplicity, prescription is used for the rest of the document.

- The study drugs will be identified through their Anatomical Therapeutic Chemical (ATC) code (see [Annex 3](#)) and will include heparins, VKAs and other DOACs in addition to rivaroxaban oral suspension.
- Following variables will be extracted from the data sources:
 - Active substance
 - Route of administration
 - Date of prescription issuance (or filling)
 - Prescribed drug amount or days' supply
 - Prescribed daily dose (if available)
- Patients will be classified into two exposure categories: the exposed will include patients with rivaroxaban oral suspension, and the unexposed will include patients receiving all other study drugs consolidated in a single group as SOC.
- Following the index date, patients will contribute follow-up time and safety/effectiveness event outcomes to their respective exposure category(ies) until they are censored (see [Section 9.2.2](#)).

Following definitions of the variables related to exposure will be used:

- **Treatment episode by agent:** this will include rivaroxaban, heparins, VKAs, and other DOACs.
 - For each agent with fixed dose, and whenever information is available, the duration of the episode will be based on days of supply, by summing the lengths of individual consecutive prescriptions of the respective agent. Drug stockpiling will be accounted for: in case of overlapping prescriptions for the same agent (i.e., the next prescription is recorded before the end of the prior prescription supply), the overlap will be added to the end date of the second prescription.
 - For agents where the dose is not fixed but titrated continuously over time according to body weight (rivaroxaban oral suspension) or to a biomarker (VKAs), the duration of a treatment episode will be based on the actual distribution of intervals between filled prescriptions.
 - For all agents, a grace period of 30 days will be used. Thus, a treatment episode will be considered discontinued if a gap >30-day grace period is observed between consecutive prescriptions of the same agent. A 30-day period will be added at the end of the treatment episode of each agent to account for a carry-over effect unless a drug switch is observed.
- **Drug switch:** defined whenever a prescription of another anticoagulant agent is recorded during a treatment episode of the prior anticoagulant agent.
- Treatment episodes for the individual SOC agents that are overlapping or separated by less than the 30-day grace period will be collapsed into a single SOC treatment episode.

- **Anticoagulant treatment period:** defined as a sequence of treatment episodes of rivaroxaban and SOC, i.e., from the initial treatment episode of the first agent at index date and all potential consecutive switch(es) to other agents. An anticoagulation treatment period will be considered discontinued when all study drugs of interest are discontinued.

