9.2.2. Study time frame

9.2.2.1. Index date and follow-up

The index date will be the day of initiation of any anticoagulation therapy (rivaroxaban oral suspension or SOC). Patients will be assigned to two exposure categories, rivaroxaban or SOC, according to their actual use of the respective anticoagulation therapy. They may contribute time at risk to more than one exposure category if they switch from one to the other. More specifically, patients will be allowed to switch multiple times between SOC and rivaroxaban and contribute time accordingly to both exposure categories, as long as the same anticoagulant treatment period is continuing.

Patients will be followed from the index date to the earliest of the following censoring criteria:

- End of the anticoagulation treatment period, i.e., discontinuation of all study drugs (rivaroxaban and SOC),
- Death,
- Disenrollment/de-registering/emigration or last available data,

- End of the study period.

Moreover, patients will be followed until the first occurrence of each safety/effectiveness outcome event, with time at risk defined separately for each outcome analysis.

If patients have another initiation of anticoagulant therapy (SOC or rivaroxaban) for a VTE diagnosis before the age of two years, i.e., another qualifying anticoagulant treatment period for a recurrent VTE observed during the inclusion period for which they fulfil all inclusion and exclusion criteria (including a 6-month washout period), they will be allowed to enter the study cohort again, with a new index date.

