Sweden	MBR, NPR, PDR, Cause of death register	National health registers	10.3 million	100%	14 days-12 months	ATC	Prescribed drugs for outpatient use, dispensed drugs through retail pharmacies, use of OTC drugs, reimbursed drugs	ICD-10	Inpatient care and specialized outpatient care
France	SNDS	Claims database	66 million	99%	3-7 months	ATC, UCD, CIP	Dispensed drugs through retail pharmacies, reimbursed drugs, some costly drugs administered in hospital	ICD-10	Inpatient care, some ambulatory long-term diseases, all procedures
Spain (Catalonia)	SIDIAP	EMR database	5.6 million	74% (from Catalonia)	12 months	ATC	Primary care prescriptions, drugs dispensed through retail pharmacies. Possible linkage with hospital pharmacy drugs databases	ICD-9, ICD-10-CM	Primary care linked to hospital admissions and deaths

ATC = Anatomical Therapeutic Chemical (Classification System); CIP = Club Inter-Pharmaceutique; CM = Clinical Modification; EMR = Electronic Medical Records; ICD = International Classification of Diseases; MBR = Medical Birth Register; NPR = National Patient Register; PDR = Prescribed Drug Register; RMPS = Register of Medicinal Products Statistics; SIDIAP = Sistema d'Informació per al Desenvolupament de l'Investigació en Atenció Primària; SNDS = Système National Des Données De Santé; SMR = Hospital Patient Medication Register; UCD = Unité Commune de Dispensation.

The feasibility of study objectives is summarized in [Table 4](#).

Table 4: Feasibility of study objectives in the data sources

Data sources	Danish national registers	SNDS	SIDIAP	Swedish national registers
Primary objectives				
To describe clinical characteristics and demographics of patients using anticoagulation therapy for the treatment of VTE (rivaroxaban oral suspension or SOC)	Yes	Yes	Yes	Yes
To describe use of anticoagulation therapy (including selected drug, dose, and duration) for treatment of VTE	Yes ^a	Yes	Yes ^a	Yes
To describe the incidence and severity of bleeding (major bleeding, and CRNM bleeding) according to anticoagulation therapy (rivaroxaban oral suspension or SOC)	BT ^b	Yes	BT ^b	BT ^b
Secondary objectives				
To describe time trends in patient characteristics and anticoagulation treatment patterns at the population-level over the study period	Yes ^a	Yes	Yes ^a	Yes
To describe the incidence of recurrent symptomatic VTE according to anticoagulation therapy (rivaroxaban oral suspension or SOC)	BT ^b	BT ^b	BT ^b	BT ^b

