is also possible that a bleeding occurs while the child is already hospitalized for another reason being reported as the primary diagnosis. To mitigate this risk of misclassification, two definitions will be considered for the bleeding outcomes: in the main analysis, a sensitive approach considering all appropriate bleedings reported as primary, related, or associated diagnoses will be used as the primary definition to capture all bleedings that might represent a major bleeding or a CRNM bleeding. By increasing specificity, a sensitivity analysis restricted to those bleeding events reported as *primary* diagnoses during hospitalization will inform on the robustness of study findings.

- Recurrent symptomatic VTE. Children are likely to come to a specialist/hospital for a control visit or something related to their first VTE. On this occasion they might be recorded with a diagnosis of VTE even if this does not represent a recurrent VTE event. In order to minimize this risk of misclassification, the outcome of recurrent VTE will be restricted to VTE diagnoses recorded in inpatient setting, thus excluding control visits for VTE which most likely occur in secondary outpatient care. However, a risk of misclassification remains for children hospitalized for a long period or for other reasons than the index VTE, where it might be difficult to distinguish a recurrent VTE event from the index VTE. For this reason, the use of a primary definition of VTE diagnoses, including all primary/main and secondary diagnoses codes, and a secondary more specific definition restricted to primary VTE diagnoses reported through hospitalization will allow to test the robustness of the findings.

Other limitations

- **Impact of the small sample size**

The number of available children aged under two years with VTE is expected to be very low in most data sources due to VTE being a rare event in this population. For this reason, all analyses will be descriptive and no confirmatory comparison between exposure categories will be performed.

To comply with GDPR, cell suppression is required to mitigate the risk of re-identification in most countries. Consequently, this is a major limitation for analyses in most data sources, except SNDS in France. Besides, due to the small sample size and low frequency of the safety and efficacy outcomes, it is expected that these analyses should only be feasible in the SNDS.

- **Missing data**

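### In SNDS and Sweden the 30-day refill-gap rule counts unseen inpatient treatment as time off drug, so a child treated through a long post-index stay is classed as discontinued and censored

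*Protocol*

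**What the plan says.** Section 9.3.1 sets one discontinuation rule for every agent and data source: "a treatment episode will be considered discontinued if a gap >30-day grace period is observed between consecutive prescriptions of the same agent". It then extends exposure: "A 30-day period will be added at the end of the treatment episode of each agent to account for a carry-over effect", unless a switch is seen. Fixed-dose agents have their episode length built from days of supply. For rivaroxaban suspension and VKAs, "the duration of a treatment episode will be based on the actual distribution of intervals between filled prescriptions"; the Protocol does not say which point of that distribution is used.

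Follow-up stops once no study drug is being taken. The first criterion in section 9.2.2.1 begins "End of the anticoagulation treatment period, i.e., discontinuation of all study drugs (rivaroxaban and SOC". Sections 9.2.2.1 and 9.2.3.1 allow a child back only as a new initiation: no recorded anticoagulant for 6 months (or since birth if younger than 6 months), an inpatient VTE code in the preceding 30 days, and age under two.

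On data, section 9.9 says that "inpatient drug data is not captured in SNDS and in Swedish national registers, which represents a risk of exposure underestimation", and that in those sources "the information on anticoagulation therapy and its duration will be based on outpatient prescriptions only". The exception in Table 3 for SNDS is "some costly drugs administered in hospital". The remedy offered for unobserved hospital time is to place the index date at the first observed record.

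**The concern.** In these two sources a child admitted during follow-up has no dispensings while the hospital supplies the drug. The gap rule cannot tell this from stopping treatment. If the stay is long enough, the episode closes, the treatment period closes with it, and the child is censored while still treated. A fill on discharge does not reopen the period.

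Section 9.9 deals with unobserved hospital treatment before the first record, not with admissions after it. The exposure sensitivity analysis in section 9.7.6.1 keeps only the first agent episode and adds carry-over. It is about switching and uses the same gap rule.

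Duration and sequence of therapy are primary descriptive results, and false discontinuations distort them directly. Both bleeding outcomes are also defined from hospital stays (section 9.3.2.1.3), so exposure goes unseen in the setting where the outcome is recorded. SNDS is the only source in which sections 9.5.2 and 9.7.8 expect the outcome analysis to be feasible.

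**Working it through.** **1. Size of the two sources (Table 6, average estimates).** The Protocol's own figures reproduce. Mean market share is (10 + 32 + 38 + 42 + 50 + 30)/6 = 33.67%. SNDS: 650 × 0.3367 = 218.8 (stated 219). Sweden: 98 × 0.3367 = 33.0 (stated 33).
- All children: (650 + 98)/846 = 748/846 = 88%.
- Rivaroxaban users: (219 + 33)/285 = 252/285 = 88%.

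**2. Day count of the rule.** Assumptions: the child is treated throughout the stay, the same agent is filled on discharge, and the gap runs from end of supply to next fill (the lenient reading). Let A be days of supply left at admission and L the length of stay.
- Apparent gap = L − A. The episode ends if L − A > 30, that is, if L > 30 + A.
- Follow-up then stops at day A + 30 after admission (supply plus carry-over).
- Treated inpatient days lost = L − (A + 30), plus all treated time after discharge.

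| A (days) | Stay that ends the episode | Gap for a 60-day stay | Follow-up stops on day | Treated inpatient days lost |
|---|---|---|---|---|
| 0 | over 30 | 60 | 30 | 30 |
| 14 | over 44 | 46 | 44 | 16 |
| 28 | over 58 | 32 | 58 | 2 |

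Carry-over cannot rescue the episode. It equals the grace period, so any fill that fails the gap test also comes after carry-over has ended.

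**3. Re-entry.** Assume the last fill covered 28 days. The discharge fill then comes L + 28 − A days after it: 88, 74 and 60 days for the three rows, against a washout of about 182 days. The washout is met only if L ≥ 154 + A, that is 154, 168 or 182 days (about 5 to 6 months). An inpatient VTE code in the preceding 30 days is needed as well.

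**4. Rivaroxaban suspension and VKAs.** Here A is not days of supply. If each fill is assigned D days and admission comes s days after the last fill, A = D − s and the critical stay is 30 + D − s. With s = 14, an assumed D of 28 gives 44 days and an assumed D of 60 gives 76 days. The mechanism is the same, but the threshold moves with a choice that the Protocol does not specify.

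**5. Direction for bleeding.** With e1 events in retained time T1 and e2 in lost time T2, the reported rate is e1/T1 and the full rate is (e1 + e2)/(T1 + T2). The reported rate is too low only if e2/T2 > e1/T1. The Protocol gives no figure for e2/T2.

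**6. With inpatient days left out.** Remaining supply is carried to discharge. A fill on discharge gives a gap of 0 for every stay tried (20 to 200 days), and no episode is ended.

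**The case against.** The strongest reply is that this belongs in the SAP. Section 9.7.1 leaves exposure definitions to a SAP written before extraction, which could add a hospital-bridging rule. That is true, but section 9.3.1 already fixes the gap rule for all agents. A SAP that follows it literally reproduces the problem, and one that adds bridging changes a definition the Protocol has set.

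Section 9.9 does concede exposure underestimation in general terms. Its discussion and its remedy, however, concern initial treatment.

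Several limits on size stand. In these two sources the index date is the first observed record, essentially an outpatient one, so a long initial VTE admission before that record is outside follow-up. Only later stays longer than 30 days plus remaining supply matter. Carry-over covers the early part of a stay, and a bleed that causes admission while the child is at risk is counted.

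Carrying a child as exposed in hospital has its own error, since the Protocol accepts that drugs may be switched there unseen. The choice is between two misclassifications, which is why both results should be shown.

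A reader might also infer more than the Protocol supports:
- *That 88% of children are affected.* That is the share of children held by the two sources.
- *That bleeding incidence is biased downwards.* Children with long stays may well bleed more, but lost person-time offsets lost events (step 5), and no figure settles it.
- *That the SNDS bleeding count would become unreportable.* The expected 12 rivaroxaban bleeds have a stated range of 5 to 20, which already straddles the suppression limit of ten, and they pool two separate outcomes. Nothing indicates how many would be lost.
- *That section 9.9 admits the problem when it mentions long hospital stays.* That remark concerns telling a recurrent VTE from the index VTE.

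**Conclusion.** The point holds as a defect in the stated exposure rule. In SNDS and Sweden, a child treated throughout a post-index stay longer than 30 days plus remaining supply is classed as discontinued and censored. Treated time after discharge is lost, except in the narrow case where the washout has elapsed and the other entry criteria are met. Shortened duration and false discontinuation follow directly. An effect on bleeding incidence is possible, with a plausible but unproven direction.

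The number of children affected cannot be computed, because the Protocol gives no readmission or length-of-stay figures. For rivaroxaban suspension and VKAs the effect also depends on the unspecified refill-interval choice. The day counts rest on the assumptions in steps 2 and 3. The change is cheap and worth making before data extraction.

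**What to change.** In section 9.3.1, for any source without inpatient drug data, leave post-index inpatient days out of both supply consumption and the 30-day gap. Keep the child in the last observed exposure category during the stay. Do not make this conditional on a later refill, since exposure would then depend on surviving to discharge and resuming treatment.

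Add admission and discharge dates to the extraction list in section 9.3.1, which does not name them. Annex 3 shows that PMSI and the Swedish NPR hold stay dates.

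Report treatment duration, discontinuation and bleeding incidence under both this rule and the unadjusted one, and state the number of children and the person-time that differ. This supplies the size that cannot be computed now.

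The cost is Protocol and SAP wording, two date fields per stay and a little programming. The downside is that a drug stopped or switched in hospital stays in the last observed category until discharge; comparing the two sets of results shows how much that matters.
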